10. STATISTICAL ANALYSIS

10.1 STUDY DESIGN

This will be a double blind, randomized, placebo controlled, multicenter, parallel-group Phase III trial comparing the efficacy and safety of Xilonix™ plus best supportive care (BSC) to placebo plus BSC. Consented eligible subjects will be enrolled and randomly assigned to treatment arm or placebo arm with 2:1 ratio respectively. Subjects randomized to treatment arm will receive Xilonix™ and those in control arm will receive placebo via intravenous infusion every 2 weeks (one cycle) plus BSC. Total study duration will be 18 months. An Independent Data Monitoring Committee will be formed prior to the study initiation to monitor the safety during study, as well as to evaluate the efficacy and safety results at the time of the protocol-specified interim analysis.

10.2 STUDY ENDPOINTS

10.2.1 Primary Efficacy Endpoint:

Overall survival (OS) will be the primary endpoint of this study survival time will be defined as the duration from the date of randomization until death. Subjects who are alive at the end of follow-up will be censored and survival time will be defined as time from randomization to censor date. The overall survival between the Xilonix™ + BSC group and placebo + BSC group will be compared using an unadjusted log-rank test.

10.2.2 Secondary Endpoints:

Secondary efficacy variables will include change in lean body mass (LBM) measured by dual-energy X-ray absorptiometry (DEXA) scans, change in Quality of Life assessed through the cancer-specific EORTC QLQ-C30 questionnaire, stabilization of platelet counts, progression free survival (PFS), objective response rate (ORR) and disease control rate (DCR).

10.2.3 Exploratory Endpoint:

Clinical Response Rate (CRR) will be the exploratory endpoint for this study. This will be a composite measure assessing the change in LBM, fatigue, pain, and appetite from baseline to week 8. Clinical response will be defined as, 1) Improvement or stabilization (≥ 0 kg change) of LBM as assessed by DEXA scan, and 2) Improvement or no worsening (≤ 0 score point change; low scores reflect better functioning and lower symptom distress) on any two of the three symptom scale measures (fatigue, pain, appetite) of EORTC QLQ-C30. Patients missing the follow-up assessment will be considered non-responders.

10.2.4 Safety Endpoint:

Safety endpoints will be evaluated by monitoring adverse events from clinical and laboratory reporting. Adverse events will be classified according to the National Cancer Institute Common Terminology Criteria for Adverse Events (NCI-CTCAE). Significant trends in the distribution and severity of the adverse events across the study groups will be assessed.

10.3 SAMPLE SIZE AND POWER

Prior research has reported a median survival of 4.6 months among refractory, metastatic colorectal cancer patients with BSC in a comparable patient cohort. On the other hand, as observed in the colorectal cancer cohort of our phase I/II trial, the median survival was 6.7 months for all enrolled colorectal cancer patients and 8.7 months for the per-protocol population. Using a conservative approach, the current study is designed to detect at least 30% improvement in median OS in treatment arm (6.0 months, hazard rate in treatment arm (h_1)=0.116)) compared to the control arm (4.6 month, hazard rate in control arm (h_0)=0.151)). We propose to test the null hypothesis for hazard ratio (h_1/h_0) =1 and alternative hazard ratio ≤ 0.767 . With a 2:1 allocation ratio and 5% oversampling, a total of 600 subjects (400 and 200 in treatment and control arm respectively) will be required to detect the 30% increase in median survival (from 4.6 to 6.0 months, hazard ratio 0.767) with one-sided Type I error probability (α) of 0.025, and 80% power ($1-\beta=0.80$). The total number of 552 deaths during the 18 month follow-up in the overall study population will provide the above power. The survival curves will be estimated with the Kaplan–Meier method and compared for statistical significance by log-rank test.

In contrast to a fixed-sample trial, where the data is analyzed at end of the study, we propose a group sequential design that provides for interim analyses before completion of trial while maintaining the specified overall Type I and Type II error probabilities.

The trial will have three stages (two interim, one final). As determined based on alpha spending function of O'Brien and Fleming sequential group design (O'Brien PC, Fleming TR, 1979), survival analyses will be performed after 276 (50%), 414 (75%) and 552 (100%) deaths at the respective stages. The efficacy and futility stopping boundaries will be computed separately.

The criteria for the early termination for efficacy (rejection of null hypothesis) or to accept the null hypothesis will be based on the group sequential design. If the test statistics crosses the pre-specified boundaries for type I error (0.0029, 0.010, and 0.012; cumulative alpha of 0.0029, 0.013, and 0.025 respectively) the trial will stop for efficacy. Otherwise, the trial continues to the next stage. The beta levels for stopping the trial for accepting the null hypothesis will be included in the detailed statistical analysis plan for the Independent Data Monitoring Committee (IDMC).

If efficacy is established at an interim analysis, enrollment will be stopped and the control group will be allowed to crossover. All subjects will be followed up until death, loss to follow-up, or termination of the study.

Randomization Strategy:

A central randomization scheme with Interactive Web Response System (IWRS) will be employed to facilitate effective randomization and allocation concealment. The scheme will involve a block randomization technique, randomly assigning participants within blocks based on a 2:1 allocation ratio. The randomization sequence will be generated using Oracle Clinical Remote Data Capture application (Oracle Corporation, Redwood City, CA, USA).

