Subjects who are alive at the analysis time point will be censored, and survival time will be defined as time from randomization to censor date. Patients, who are lost to follow-up or discontinued, will be censored at time of last contact. A censoring variable will be created identifying censored observation. The primary endpoint, overall survival, will be summarized by Kaplan-Meier method and compared between the treatment groups using un-adjusted log-rank test. The median survival, cumulative survival probability and 95% confidence interval (CI), calculate by log-log transformation and 25th and 75th percentiles, will be reported according to treatment groups. Kaplan-Meier curves will be generated plotting the survival probability and probability of occurrence in time. Number of patients at risk on various time intervals will be presented on the curve. The type I error rate to be used for determining statistical significance of the primary outcome is defined in section 10.3 "interim efficacy analyses".

A secondary supportive analysis will be performed comparing survival probability across treatment groups, stratified by age (dichotomizing by median), gender, ECOG performance status, KRAS mutation status, regorafenib and bevacizumab treatment failure status, and number of prior antineoplastic therapies. Survival probability and 95% CI for treatment groups will be reported for by each stratum.

A multivariate Cox proportional hazards regression (CPH) method will be used for assessing independent predictors of OS after adjusting for potential confounders. Selection of covariates will primarily be based on a priori knowledge, and include age (continuous scale), prior cancer therapy (number of regimens will be entered on continuous scale), ECOG performance status (categorical 0-1, 2), baseline IL-1 RA level and KRAS mutation status (coded as no=0, yes=1), and baseline body weight (continuous scale). A backward selection method will be used for variable selection; the p-value threshold will be set at 0.10. Proportional-hazard assumption will be tested by Schoenfeld residual analysis. The hazard ratio (HR) and 95% CI will be computed and presented in the results. The CPH analysis will be exploratory in nature. Receiver operating characteristic (ROC) analysis will be performed to identify the optimal cut-off of baseline IL-RA level that best discriminate overall survival.

Efficacy Evaluation: Secondary Efficacy Measures

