Prior research has reported a median survival of 4.6 months among refractory, metastatic colorectal cancer patients with BSC in a comparable patient cohort. On the other hand, as observed in the colorectal cancer cohort of our phase I/II trial, the median survival was 6.7 months for all enrolled colorectal cancer patients and 8.7 months for the per-protocol population. Using a conservative approach, the current study is designed to detect at least 30% improvement in median OS in treatment arm (6.0 months, hazard rate in treatment arm (h_1)=0.116) compared to the control arm (4.6 month, hazard rate in control arm (h_0)=0.151). We propose to test the null hypothesis for hazard ratio (h_1/h_0)=1 and alternative hazard ratio ≤ 0.767 . A total of 552 deaths will be required to detect the 30% increase in median survival (from 4.6 to 6.0 months, hazard ratio 0.767) with one-sided Type I error probability (α) of 0.025, and 80% power (1-

beta=0.80). With a 2:1 allocation ratio and 5% oversampling, a total of 600 subjects (400 and 200 in treatment and control arm respectively) with 18 month follow-up of the overall study population will provide the required number of events (deaths). The survival curves will be estimated with the Kaplan–Meier method and compared for statistical significance by an unadjusted log-rank test.

5.1 Interim Efficacy Analyses:

Two interim efficacy analyses will be conducted before the final analysis of overall survival. As determined based on alpha spending function of O'Brien and Fleming sequential group design (O'Brien PC, Fleming TR, 1979), survival analyses will be performed after 276 (50%), 414 (75%) and 552 (100%) deaths at the respective stages. After the required number of events for the specific interim analysis has occurred, the database will be frozen for planned statistical analysis.

The criteria for the early termination for efficacy (rejection of null hypothesis) or to accept the null hypothesis will be based on the group sequential design. If the test statistics crosses the pre-specified boundaries for type I error (alpha cut-off 0.0029, 0.0121, and 0.025 at the first, second interim or final analysis respectively) the trial will stop for efficacy. Otherwise the trial continues to the next stage.

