The cumulative p value for the acceptance boundary (beta) will be 0.25 and 0.08 at the first and second interim respectively. If efficacy is established at an interim analysis, enrollment will be stopped and the control group will be allowed to crossover. All subjects will be followed up until death, loss to follow-up, or termination of the study. SAS codes for O'Brien and Fleming sequential group design will be included in the Interim Analysis Plan. TFL shells for interim analysis are provided in the Appendix section. The decision rule with interim monitoring will be as follows:

1. If type I error probability (alpha) \leq the above specified cumulative alpha level at the given stage, trial will stop for efficacy
2. Else, if the p value \geq the above specified beta levels the trial will stop for accepting null hypothesis
3. Else the trial will continue to the next stage
4. At final analysis, if alpha is ≤ 0.025 then declare efficacy; otherwise accept the null hypothesis.

The Trial Statistician, who is independent from the study statistician, will conduct these interim analyses as well as the end-of-study final analysis. The Trial Statistician will be responsible for presenting the unblinded interim data to the IDMC. Prior to completion of the trial, unblinded access to the interim efficacy data will only be available to the IDMC for review and the committee has the responsibility of making recommendations to the sponsor based on this data.

6 Randomization Strategy

A central randomization scheme with Interactive Web Response System (IWRS) will be employed to facilitate effective randomization and allocation concealment. The scheme will involve a block randomization technique, randomly assigning participants within blocks based on a 2:1 allocation ratio to the Xilonix™ and placebo arm respectively. After confirmation of eligibility, the study coordinators at the clinical site will complete the randomization eCRF indicating the patient has met inclusion criteria and is ready to be randomized. This step will initiate an IWRS procedure, which will assign the next available sequential randomization number specifying the arm allocation. The randomization sequence will be generated using Oracle Clinical Remote Data Capture (OC RDC) application (Oracle Corporation, Redwood City, CA, USA). The randomization code and the study arm assignment will be maintained inside the RDC system. The randomization will not be stratified on any factor.

7 Statistical Methods

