8.4.1 Primary Efficacy Endpoint

Subjects who are alive at the data inclusion cutoff date for the analysis will be censored at that date and survival time will be defined as time from randomization to censor date. Patients lost to follow-up and untraceable for survival status will be censored on the last date subject was known to be alive or lost to follow-up. A censoring variable will be created identifying a censored observation. The primary endpoint, overall survival, will be summarized by Kaplan-Meier method and compared between the treatment groups using an un-adjusted log-rank test. The median survival, and cumulative survival probability along with 95% confidence interval (CI) calculate by log-log transformation and 25th and 75th percentiles will be reported according to randomization arms. Kaplan-Meier curves will be generated plotting the estimated survival density function over time. Number of patients at risk on various time intervals will be presented on the curve. The type I error rate to be used for determining statistical significance of the primary outcome is defined in section 5.1 “Interim Efficacy Analyses”.

The primary efficacy analysis will also be conducted for the PP population.

A secondary supportive analysis will be performed comparing survival probabilities across treatment groups, stratified separately by age (dichotomizing at median), gender, ECOG performance status, KRAS mutation status and prior treatment with regorafenib, and number of prior antineoplastic therapies. Survival probabilities and 95% CI for the 25th, median and 75th percentiles will be reported by treatment groups and stratum. No multiplicity adjustment will be made for this supportive analysis.

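### Protocol 10.3 prints stage-wise alpha as the efficacy boundaries, SAP 5.1 prints the nominal p limits of the same design under a cumulative label, and neither says the futility stops behind the final 0.025 limit are binding

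*Protocol*

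**What the plan says.** Both documents plan looks at 276, 414 and 552 deaths (50%, 75% and 100% of information) with an O'Brien-Fleming design, one-sided alpha 0.025 and 80% power.

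- **Protocol 10.3** stops for efficacy if the test statistic crosses "boundaries for type I error (0.0029, 0.010, and 0.012; cumulative alpha of 0.0029, 0.013, and 0.025 respectively". It gives no futility limits, deferring them to the SAP, and says "The efficacy and futility stopping boundaries will be computed separately". A trial that does not cross for efficacy goes on to the next stage.
- **Protocol 10.4** points back: "The type I error rate to be used for determining statistical significance of the primary outcome is defined in section 10.3".
- **SAP 5.1** gives "alpha cut-off 0.0029, 0.0121, and 0.025 at the first, second interim or final analysis respectively", followed by "Otherwise the trial continues to the next stage". It sets acceptance limits of 0.25 and 0.08 at the two interims and describes them as a cumulative p value (beta). Decision rule 1 compares the result with "the above specified cumulative alpha level at the given stage, trial will stop for efficacy". Rule 2 compares p with "the above specified beta levels the trial will stop for accepting null hypothesis". Rule 4 declares efficacy at the final look at 0.025 or less. The IDMC makes recommendations to the sponsor.
- **SAP 8.4.1** points to its own section: "The type I error rate to be used for determining statistical significance of the primary outcome is defined in section 5.1".

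**The concern.** The second and third efficacy figures differ between the documents (0.010 and 0.012 against 0.0121 and 0.025), and each document names its own section as the significance rule for the primary endpoint. A final one-sided p of 0.02 would be a success by SAP rule 4 and a failure by the protocol's printed boundary.

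The SAP's own set raises a second question. Two efficacy looks followed by a final test at the full 0.025 would ordinarily exceed 2.5% overall. It can hold only if stops for futility remove some of the paths that would otherwise reach a false positive. Whether that credit may be taken depends on the futility rule being binding, and neither document states this.

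**Working it through.** **Inputs.** Information fractions t = 0.5, 0.75, 1.0; 552 deaths; 2:1 allocation; medians 4.6 and 6.0 months (Protocol 10.3). Efficacy p limits 0.0029, 0.0121, 0.025 and futility p limits 0.25, 0.08 (SAP 5.1). All p values are one-sided.

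**Method.** The log-rank z at look k is treated as normal with mean θ√t and the usual independent increments. Stage probabilities come from recursive numerical integration. The drift under the design alternative is

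θ = √(552 × 2/9) × ln(6.0/4.6) = 11.076 × 0.2657 = 2.943.

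**Step 1: are the SAP limits an O'Brien-Fleming set?** The z limits are 2.759, 2.254 and 1.960. Multiplying by √t gives 1.951, 1.952 and 1.960, constant to rounding. They are therefore nominal p limits of that family. Solving the design with both stops enforced, for alpha 0.025 and power 0.80, gives nominal efficacy limits 0.0029, 0.0121, 0.0254, futility limits 0.249 and 0.080, and 554 deaths at a hazard ratio of 4.6/6.0. This reproduces the plan's 552 closely.

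**Step 2: reproduce the protocol's figures from the SAP limits, futility obeyed.**

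| Deaths | Nominal p limit | Stage alpha | Cumulative alpha | Futility p limit | Cumulative beta |
|---|---|---|---|---|---|
| 276 | 0.0029 | 0.0029 | 0.0029 | 0.25 | 0.080 |
| 414 | 0.0121 | 0.0101 | 0.0130 | 0.08 | 0.149 |
| 552 | 0.025 | 0.0118 | 0.0248 | n/a | n/a |

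The stage column is the protocol's first list and the cumulative column is its second, to rounding. Power is 79.8%. Two SAP labels fail here: cumulative alpha at look 2 is 0.0130, not 0.0121, and cumulative beta is 0.080 then 0.149, not 0.25 then 0.08.

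**Step 3: use each printed set as p limits.**

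| Limits | Futility | Type I error | Power |
|---|---|---|---|
| Protocol 0.0029/0.010/0.012 | both obeyed | 1.65% | 74.9% |
| Protocol 0.0029/0.010/0.012 | both ignored | 1.77% | 77.5% |
| SAP 0.0029/0.0121/0.025 | both obeyed | 2.48% | 79.8% |
| SAP | only the first ignored | 2.60% | |
| SAP | only the second ignored | 2.71% | |
| SAP | both ignored | 2.95% | |

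A simulation of 4 million trials gave 2.49%, 2.60%, 2.72% and 2.95% for the four SAP rows.

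**Step 4: how often would the futility question arise?** With a hazard ratio of 1, the futility limit is met in 75.0% of trials at look 1 and a further 17.8% at look 2. Under the design hazard ratio the total is 14.9%.

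**Step 5: how much does the cumulative label matter by itself?** Using 0.013 as the look-2 p limit gives 2.52% with futility obeyed, which is a small effect.

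**The case against.** The best counter-argument is that an informed reader can decode both documents. The protocol prints the running total beside its first list, so that list identifies itself as stage-wise alpha, and SAP rule 4 sets the final test at 0.025. The cross-reference in Protocol 10.4 also cites an interim-analysis heading that exists in the SAP and not in Protocol 10.3, which weakens the claim that 10.3 is meant to be operative. On futility, SAP rule 2 is mandatory in wording, and the SAP's table shell lists a futility stop as an action at each stage, so futility is binding in effect. An IDMC only recommends on efficacy too. Binding status may also be stated in the Interim Analysis Plan or the IDMC charter, which are not available here.

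Much of this is fair. Followed as an ordered rule, SAP 5.1 holds 2.48% with about 80% power, and the mislabelling of 0.25 and 0.08 changes no decision. But decoding the protocol's list shows only its scale. It yields no usable p limit for looks 2 and 3 without the futility limits, which the protocol does not give. The mandatory wording of rule 2 also stands against the protocol's statement that the two boundary sets are calculated separately, and against sentences in both documents that send any trial not crossing for efficacy to the next stage. Neither document says the final 0.025 depends on futility being enforced.

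**Conclusion.** The concern holds and should be fixed. The decision thresholds for the primary endpoint are wrong as written in Protocol 10.3. Applied literally, they cost about 4.9 points of power (79.8% to 74.9%) and use 1.65% of the 2.5% alpha. The SAP's limits are sound if futility is enforced (2.48%), but rise to between 2.60% and 2.95% if one or both futility stops are overridden. The cumulative labels in the SAP are incorrect but matter little by themselves.

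These figures assume looks at exactly 276, 414 and 552 deaths, a normal log-rank statistic, proportional hazards with ratio 4.6/6.0, and 2:1 allocation. Using a hazard ratio of 0.767 instead moves power by no more than about 0.2 points. The SAP's final 0.025 appears to be 0.0254 rounded, or the overall alpha carried over; the difference is 2.48% against 2.50%.

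**What to change.** Put one identical table in Protocol 10.3 and SAP 5.1, with every column labelled: deaths, nominal one-sided efficacy p limit, stage alpha, cumulative alpha and nominal futility p limit.

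- 276 deaths: 0.0029; 0.0029; 0.0029; 0.25.
- 414 deaths: 0.0121; 0.0101; 0.0130; 0.08.
- 552 deaths: 0.025; 0.0118; 0.0248; no futility limit.

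In Protocol 10.3, replace 0.010 and 0.012 as the boundaries to cross with the nominal limits, and correct the sentence about separate computation. In SAP 5.1, remove the word cumulative from rule 1 and from the futility sentence. In both documents, make continuation to the next stage subject to the futility rule.

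Then state the status of futility:

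- **Binding:** keep 0.0029, 0.0121 and 0.025. The cost is wording only.
- **Non-binding:** keep the interim limits and lower the final limit to 0.0196. Type I error is then 2.50% even if both futility stops are ignored. Power with futility followed falls from 79.8% to 78.4%, about 1.4 points.

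If efficacy really is to be computed separately, the efficacy-only O'Brien-Fleming limits 0.0021, 0.0097 and 0.0215 also hold 2.50%, with power 78.7% (about 1.1 points lower). That is an option, not something the documents require.

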10.4 STATISTICAL ANALYSIS PLAN

The primary efficacy analysis will be conducted for the intent-to-treat (ITT) and Per-protocol (PP) population. The ITT population will consist of all randomized patients. The PP population will be defined as those patients in the ITT set who are compliant with the study protocol.

Given the nature of change to the study design, patients enrolled prior to modification (V3.0) will be excluded from the primary efficacy analysis. Those patients will be analyzed separately.

Patient Characteristics and Baseline Comparisons:

The ITT population will be included for analysis of demographic and baseline findings. Data will be summarized for each treatment group, i.e. Xilonix™ and placebo arm. Descriptive analysis will be performed summarizing age, gender, Eastern Cooperative Oncology Group (ECOG) status, co-morbidities, cancer therapy, and other relevant baseline risk factors by treatment group. Baseline biochemistry, hematology data will be summarized in separate tables. Continuous variables will be reported as mean \pm standard deviation (SD), median and inter-quartile range (IQR) for non-normal data. The categorical variables will be reported as number of cases (n) and percentage. The baseline characteristics will be compared across the groups for overall difference by using independent-samples t-test for continuous variables and chi-square test (Fisher's exact if $n < 20$) for categorical data. Normality of the analysis variables will be tested using Shapiro-Wilks test. If the Shapiro-Wilks test is significant, continuous data will be compared using Wilcoxon (for paired data) and Mann-Whitney nonparametric test. Correlation between parameters was evaluated using Spearman correlation coefficients. A two-tailed p value of < 0.05 will be considered statistically significant for the descriptive summary statistics.

Efficacy Evaluation: Primary Efficacy Endpoint

Subjects who are alive at the analysis time point will be censored, and survival time will be defined as time from randomization to censor date. Patients, who are lost to follow-up or discontinued, will be censored at time of last contact. A censoring variable will be created identifying censored observation. The primary endpoint, overall survival, will be summarized by Kaplan-Meier method and compared between the treatment groups using un-adjusted log-rank test. The median survival, cumulative survival probability and 95% confidence interval (CI), calculate by log-log transformation and 25th and 75th percentiles, will be reported according to treatment groups. Kaplan-Meier curves will be generated plotting the survival probability and probability of occurrence in time. Number of patients at risk on various time intervals will be presented on the curve. The type I error rate to be used for determining statistical significance of the primary outcome is defined in section 10.3 "interim efficacy analyses".

A secondary supportive analysis will be performed comparing survival probability across treatment groups, stratified by age (dichotomizing by median), gender, ECOG performance status, KRAS mutation status, regorafenib and bevacizumab treatment failure status, and number of prior antineoplastic therapies. Survival probability and 95% CI for treatment groups will be reported for by each stratum.

A multivariate Cox proportional hazards regression (CPH) method will be used for assessing independent predictors of OS after adjusting for potential confounders. Selection of covariates will primarily be based on a priori knowledge, and include age (continuous scale), prior cancer therapy (number of regimens will be entered on continuous scale), ECOG performance status (categorical 0-1, 2), baseline IL-1 RA level and KRAS mutation status (coded as no=0, yes=1), and baseline body weight (continuous scale). A backward selection method will be used for variable selection; the p-value threshold will be set at 0.10. Proportional-hazard assumption will be tested by Schoenfeld residual analysis. The hazard ratio (HR) and 95% CI will be computed and presented in the results. The CPH analysis will be exploratory in nature. Receiver operating characteristic (ROC) analysis will be performed to identify the optimal cut-off of baseline IL-RA level that best discriminate overall survival.

Efficacy Evaluation: Secondary Efficacy Measures

Secondary endpoints, QoL score and LBM will be evaluated for the absolute change at 8 week follow-up on each measure, as well as through a responder analysis comparing objective response rate across study arms.

LBM: Patients showing stabilization or improvement from baseline (≥ 0 kg change) will be considered LBM responders. Patients experiencing LBM reduction will be defined as non-responders. Those not having a second evaluation for going off the study or any other reason, will be considered non-responder. Responder rate will be compared using Pearson chi-square test. Proportion by group, relative risk and odds ratio estimates will be presented with 95% confidence intervals (95% CI).

Absolute change will be compared between the Xilonix™ and placebo group using analysis of covariance (ANCOVA) method (SAS GLM procedure) with treatment groups as factor and baseline value as covariate. The difference in least-square means and 2-sided P values will be derived from analysis of covariance model for comparison.

EORTC: The EORTC survey results will be converted to domain specific scores using the prescribed algorithm. And scores on EORTC QLQ-C30 functional and symptom scales will be summarized according the randomization groups. Score on each scale will be summarized by study arms.

Patients showing stabilization or improvement from baseline (≤ 0 change) on any two of the three symptom scales (pain, fatigue, appetite) will be considered responders. Patients experiencing reduction or worsening will be defined as non-responders. The comparison of responder rate and absolute change will performed similar to as described for LBM.

Platelet Count: Change in platelet count from baseline to follow-up will be compared between treatment groups using the analysis of covariance method described above. The last visit cycle where at least 20 patients per group are on study will be used for follow-up data cut-off for this measure. Trend line plots displaying the median platelet count over time (visit cycles) by treatment groups will be generated..

Progression Free Survival (PFS): This will be defined as time from randomization to tumor progression or death. Patients surviving without disease progression at end of study will be censored. PFS will be compared by Kaplan-Meier method using log-rank test. Kaplan-Meier plots by treatment arm will be produced, and point estimates and 95% CIs will be summarized.

Objective Response Rate (ORR): The ORR will be estimated by dividing the total number of confirmed complete response (CR) and partial response (PR) by the total number of patients randomized. Exact 95% confidence intervals for the response rate in each treatment arm will be calculated. Best overall response (BOR), determined from the sequence of cycle responses assessed, will be used for analysis purposes. Response rates will be compared between treatment groups using a Pearson Chi-square test and Wald 95% CI will be reported.

Disease Control Rate (DCR): The DCR will be estimated by dividing the total number of confirmed CRs, PRs and stable disease (SD) by the total number of patients randomized. DCR

will be analyzed as described for RR. Best overall response (BOR), will be used for DCR analysis. Proportion of response category by group along with 95% CI will be reported.

Inferential analysis for the secondary endpoints, without multiplicity correction, will be carried out for stratification variables (age, prior therapy, ECOG performance status, KRAS mutation status, Regorafenib and bevacizumab failure status), One-way ANOVA, and Fisher's exact tests will be used to compare differences across stratification groups. Proportion by group along with 95% CI will be reported.

A two-tailed p value of <0.05 will be considered statistically significant for all secondary endpoints. SAS 9.2 or higher (SAS Institute Inc., Cary, NC) will be used for statistical analysis.

